## **8. RESEARCH QUESTION AND OBJECTIVES**

The primary objective of this exploratory meta-analysis is to evaluate the frequencies, incidence rates, and hazard ratios of lower-limb amputation (LLA) events (primary outcome) and of AEs related to amputation (secondary outcome) in patients treated with empagliflozin compared with placebo in the pooled population of the long-term studies 1245.25, 1245.110, and 1245.121 (SAF-M1), in the pooled population of studies 1245.110 and 1245.121 (SAF-M2), and in each of the 3 studies separately.

The exploratory objectives are to evaluate the frequencies of recurrent LLA events and of AEs related to recurrent LLA events and to assess the frequencies and incidence rates of patients with AEs related to amputation preceding the amputation for empagliflozin compared with placebo in SAF-M1, SAF-M2, and in each of the 3 studies separately. Further exploratory objectives are to evaluate the frequencies, incidence rates, and hazard ratios of the primary and secondary outcomes by subgroup and of the secondary outcome by grouped PTs for SAF-M1 and SAF-M2 as well as to assess details on LLA events for SAF-M2 in patients treated with empagliflozin compared with placebo.

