**1245.110 (EMPEROR-Preserved) and 1245.121 (EMPEROR-Reduced), both ongoing**

**Aim:** To investigate the safety and efficacy of empagliflozin versus placebo on top of guideline-directed medical therapy in patients with heart failure with reduced or preserved ejection fraction

**Population:** T2D and non-T2D, age ≥18 years, chronic HF (NYHA II–IV)

Figure 9.1: 1 Design of studies 1245.25, 1245.110, and 1245.121

QD/qd, once daily; T2DM, type 2 diabetes mellitus; LVEF, left ventricular ejection fraction; SoC, standard of care

\* Guideline-directed therapies

This meta-analysis will be exploratory. All analyses will be based on the treated set, which includes all patients treated with at least 1 dose of study medication (as randomised). Due to the different patient eligibility criteria (see [Section 9.2.2](#)) and methods in capturing LLA and related events (see [Section 9.3.2.1](#)), two analysis groupings will be used in the meta-analysis. SAF-M1 includes all 3 studies while SAF-M2 includes studies 1245.110 and 1245.121. All

analyses will be carried out separately for each SAF and for each study, unless otherwise indicated in [Section 9.7.1](#) and [9.7.2](#).

The primary outcomes are LLA events (see [Section 9.3.2.1](#)).

LLA events will be analysed using frequency analyses, incidence rates, Kaplan-Meier estimates, and Cox proportional hazards models to compare empagliflozin with placebo. For SAF-M2, where additional information on LLA events are collected on the eCRF, the reasons leading to LLA, the number of LLA episodes, level of LLA, etc., will be summarised.

As the primary analysis, the “on-treatment” approach will include events with an onset date within the treatment period (from first to last dose of study medication plus 7 days to account for the residual drug effect). An ITT approach will be used as a secondary analysis, which includes all events during the observation period after starting randomised treatment, regardless if the patient was taking study medication or not when the event occurred.

Since deaths are competing events to amputations, a competing risk analysis considering all-cause death and a cumulative incidence analysis will be carried out.

Subgroups by demographics, baseline medical conditions, and baseline therapies will be analysed for LLA events for SAF-M1 and SAF-M2 (see [Section 9.3.3](#) for subgroup variables).

The secondary outcomes are AEs related to amputation (see [Section 9.3.2.2](#)).

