### **9.3.2      Outcomes**

The objective of the meta-analysis is to evaluate the risk for LLA in an exploratory manner.

All outcome data, including recurrent events, are collected over the full trial period even after the first amputation event.

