Disposition, demographics, exposure	Yes	Yes	Yes	Yes	Yes
Concomitant diagnoses and therapies	Yes	Yes	Yes	Yes	Yes
Lower limb amputation					
Frequencies	Yes	Yes	Yes	Yes	Yes
Incidence rates	Yes	Yes	Yes	Yes	Yes
Time to onset analyses	Yes	Yes	Yes	Yes	Yes
Time to onset analyses with competing risk	Yes	-	-	-	-
Sensitivity analyses (heterogeneity analyses, forest plot)	Yes	Yes	-	-	-
Adverse events related to amputations (definition based on list of PTs)					
All patients					
Frequencies	Yes	Yes	Yes	Yes	Yes
Incidence rates	Yes	Yes	Yes	Yes	Yes
Time to onset analyses	Yes	Yes	Yes	Yes	Yes
Patients with amputations only, i.e. preceding events					
Frequencies	Yes	Yes	Yes	Yes	Yes
Incidence rates	Yes	Yes	Yes	Yes	Yes
Time to onset analyses (KM only)	Yes	Yes	Yes	Yes	Yes
Lower limb amputation events occurring after the first LLA event					
Descriptive Statistics (Frequency tables with absolute and relative frequencies)	Yes	Yes	Yes	Yes	Yes
Adverse Events related to amputations occurring after the first LLA event					
Descriptive Statistics (Frequency tables with absolute and relative frequencies)	Yes	Yes	Yes	Yes	Yes

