### **9.7.2 Further analysis**

#### **9.7.2.1 Further analyses of LLA events, AEs related to amputation, and details on LLA events**

##### *LLA events*

Subgroups by demographics, baseline medical conditions, and baseline therapies will be analysed for LLA events for SAF-M1 and SAF-M2 (see [Section 9.3.3](#) for subgroup variables and categorisation and [Section 9.7.2.3](#)).

An ITT approach will be used as a secondary analysis, which includes all events during the observation period after starting randomised treatment, regardless if the patient was taking study medication or not when the event occurred.

Since deaths are competing events to amputations, a competing risk analysis considering all-cause mortality and a cumulative incidence analysis will be carried out. The regression model will include the following co-variables: study, diabetes mellitus status (T1DM, T2DM, no diabetes), and treatment (all empa vs. placebo). Cumulative incidence for amputations and the competing events of deaths will also be displayed graphically.

The number of LLA episodes per patient will be summarised in a frequency table.

A listing of patients with recurrent events will be provided. Descriptive statistics (frequency tables with absolute and relative frequencies) will be provided to summarise all amputation events occurring after the first LLA event.

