Considering the potential differences in patient populations, subgroup analyses by demographic and baseline conditions will be carried out to assess any potential impact of these differences on the results (see [Section 9.3.3](#)).

For study 1245.25, LLA-related events were not pre-specified in the protocol or specifically captured on eCRF pages (see [Section 9.3.2.1](#)). Therefore, the extent of reporting may be different from studies 1245.110 and 1245.121. As details on LLA events collected in studies 1245.110 and 1245.121 (the reasons leading to LLA, the number of LLA episodes, level of LLA, etc.) are not available in 1245.25, SAF-M2 is created for the purpose of analysing these specific details.

Although approx. 14 000 patients are expected to be included in this meta-analysis (see [Section 9.5](#)), the number of studies involved is low ( $N=3$ ). The 3 studies were designed to investigate empagliflozin's effect on cardiovascular events, and not specifically designed or powered to investigate LLA events. As all 3 studies are event-driven, duration of treatment and observation will be different for each patient, which will be taken into account using "time at risk" to adjust the incidence of outcomes (see [Section 9.3.1](#)). As all 3 studies investigate patients who meet the specific study entry criteria, the patients in this meta-analysis may not exactly reflect the circumstances in which empagliflozin is used in the routine clinical practice, thereby limiting the generalisability of the results.

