4.1 OUTCOMES

In the following sub-sections all endpoints which are relevant for the meta-analysis are described.

AEs will be coded using the most recent version of the MedDRA coding dictionary. The following types of events will be distinguished.

All outcome data is collected over the full trial period even after the first amputation event. We collect all events including recurrent events during the trial period.

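### Recurrent amputations are to be tabulated for 1245.25 and SAF-M1, although Section 9.9 says episode counts are unavailable in 1245.25, and the pooled SAF-M1 percentages mix the studies differently in the two arms

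*Protocol*

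**What the plan says.** **Availability of episode counts.** Protocol Section 9.9 states that "the reasons leading to LLA, the number of LLA episodes, level of LLA, etc.) are not available in 1245.25", and gives this as the reason for creating SAF-M2. Section 9.1 takes the same line: for SAF-M2, because of the extra eCRF information, "the reasons leading to LLA, the number of LLA episodes, level of LLA, etc., will be summarised".

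**Planned recurrence analyses.** The exploratory objective in Section 8 is to "evaluate the frequencies of recurrent LLA events and of AEs related to recurrent LLA events", "for empagliflozin compared with placebo in SAF-M1, SAF-M2, and in each of the 3 studies separately". Protocol Table 9.7: 2 has a row "Lower limb amputation events occurring after the first LLA event" marked Yes in all five columns, including SAF-M1 and 1245.25. SAP Table 4.3: 1 has the same row with the same entries. In Section 9.7.2.1, under LLA events and with no limit to SAF-M2, "The number of LLA episodes per patient will be summarised in a frequency table". The same item appears again in the SAF-M2 list, and SAP Section 4.3.2.2.1 repeats this pattern.

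**Collection.** Protocol Section 9.3.2 says "All outcome data, including recurrent events, are collected over the full trial period even after the first amputation event" and SAP Section 4.1 says "We collect all events including recurrent events during the trial period". Neither makes an exception for 1245.25. SAP Appendix 6.2 describes a retrospective search of 1245.25 over each patient's whole participation. It accepts any lower-limb amputation but gives no rule for separating or counting second and later ones.

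**Pooling rule.** Protocol Section 9.7 and SAP Section 4.3 weight each study's percentage by its share of patients within the treatment group, which reproduces the crude pooled percentage. Tables show placebo, 10 mg, 25 mg and all empagliflozin.

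**The concern.** There are two linked problems.

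First, a programmer cannot tell which statement governs. If the number of episodes in 1245.25 is unavailable, amputations after the first cannot be tabulated for that study or for a pool that contains it. If it is available, the limitations section is wrong. A safety report requested by the regulator should not show recurrence figures for a study whose count its own protocol calls unavailable.

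Second, the objective is a comparison with placebo. Study 1245.25 allocated about 2:1 to empagliflozin and the heart failure studies 1:1, so the crude pooled percentages average over a different mix of studies in each arm. Any difference between studies in captured recurrence, whether from risk, follow-up or reporting, then moves the SAF-M1 comparison without any treatment effect. The weighting applies to every SAF-M1 frequency. For first amputation, however, a Cox model with study as a factor stands beside the percentage. For recurrence the plan offers only descriptive frequencies and a patient listing.

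**Working it through.** **Inputs (protocol Section 9.5).**
- 1245.25, treated: 2345 on 10 mg, 2342 on 25 mg, 2333 on placebo.
- 1245.110: about 4126 randomised 1:1. 1245.121: about 2850 randomised 1:1.
- Assumption: all randomised heart failure patients are treated (the protocol expects almost all).

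**Reproducing the stated size.** 2345 + 2342 + 2333 = 7020. 7020 + 4126 + 2850 = 13 996, which agrees with the stated approx. 14 000.

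**Study mix by arm.** Heart failure patients per arm: (4126 + 2850)/2 = 3488. The share w of 1245.25 in each tabulated SAF-M1 column is:

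| Column | From 1245.25 | Column total | w |
|---|---|---|---|
| All empagliflozin | 4687 | 8175 | 0.573 |
| Empagliflozin 10 mg | 2345 | 5833 | 0.402 |
| Empagliflozin 25 mg | 2342 | 2342 | 1.000 |
| Placebo | 2333 | 5821 | 0.401 |

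If only 95% of heart failure patients were treated, the shares would be 0.586 for all empagliflozin and 0.413 for placebo, so the imbalance does not depend on that assumption.

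**Effect on the crude ratio under no treatment effect.** Let r be the captured recurrence frequency in 1245.25 divided by that in the heart failure studies, with all treated patients as denominator. The documents give no recurrence data, so r is assumed. For a column with share w,

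ratio to placebo = (w·r + 1 − w) / (0.4008·r + 0.5992).

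For all empagliflozin at r = 0.5: (0.5733 × 0.5 + 0.4267)/(0.4008 × 0.5 + 0.5992) = 0.7133/0.7996 = 0.892.

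| r | All empagliflozin | 10 mg | 25 mg |
|---|---|---|---|
| 0.5 | 0.892 | 0.999 | 0.625 |
| 1 | 1.000 | 1.000 | 1.000 |
| 2 | 1.123 | 1.001 | 1.428 |

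At r = 0 the all-empagliflozin ratio is 0.712. That is only an extreme bound and is not expected, given the search in Appendix 6.2. The imbalance comes from the 25 mg arm, which exists only in 1245.25.

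**Other denominator.** Suppose the denominator were patients with a first amputation, with an assumed first-amputation risk of 2% in all studies and assumed recurrence of 15% in 1245.25 and 30% in the heart failure studies. The crude percentages would be 21.4% and 24.0%, a ratio of 0.89. With the two recurrence values exchanged, the ratio would be 1.12.

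**Alternatives.** With one study weight for both arms (for example 7020/13 996 = 0.502 for 1245.25), both arms give 0.502·r + 0.498, so the ratio is 1.00 at every r. A Mantel-Haenszel ratio by study also gives 1.00: if both arms of study i share frequency p_i, numerator and denominator both equal the sum over studies of p_i·n_1i·n_0i/N_i. SAF-M2 is unaffected, since 1245.110 is 59.1% of both arms.

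**The case against.** The sentence in Section 9.9 is about details collected in the heart failure studies, so it may mean only that 1245.25 lacks the structured eCRF record. The other sections that plan recurrence analyses or describe collection assume recurrence can be analysed there. Appendix 6.2 covers the whole participation period, accepts any amputation, and excludes stump revisions only when no extension of the amputation is mentioned, so later procedures were considered. This makes countability the likelier case. It does not remove the conflict, because Section 9.9 names the number of episodes itself and no counting rule is written down.

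On the pooling, several protections already exist: by-study and SAF-M2 tables, a listing of patients with recurrent events, a 10 mg column that is almost balanced against placebo, and a warning in Section 9.9 that the extent of reporting may differ. The value of r is assumed, the direction is unknown, and the shift vanishes at r = 1. It is also small against sampling error. If 0.2% to 1% of treated patients had a recurrence (an assumption), the 95% limits on the crude ratio would lie a factor of about 2.1 to 1.4 either side.

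All of this limits the consequence. It does not make the planned all-empagliflozin percentage a fair comparison with placebo, and no study-adjusted recurrence summary is planned to offset it.

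**Conclusion.** The concern holds, at minor severity. Section 9.9, and to a lesser degree Section 9.1, contradicts the objective and both analysis tables on whether repeat amputations in 1245.25 can be counted. Section 9.9 may simply be too strong, but that has to be confirmed outside these documents.

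The difference in study mix, 57.3% against 40.1%, follows from the stated arm sizes and weights. Its consequence for the ratio (0.89 to 1.12 for r between 0.5 and 2) is an illustration that rests on assumed values of r, with no known direction. The effect is confined to exploratory descriptive tables. The primary analysis of time to first amputation is not touched.

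**What to change.** 1. Confirm whether second and later amputations in 1245.25 can be counted, and align Sections 9.9 and 9.1 with Section 8, protocol Table 9.7: 2 and SAP Table 4.3: 1.
2. If they can be counted, correct the sentence in Section 9.9. Base the SAF-M1 recurrence comparison on the by-study tables already planned, or on a study-stratified summary (study weights common to both arms, or Mantel-Haenszel), instead of the crude pooled percentages.
3. If they cannot, limit the recurrent-amputation analysis to SAF-M2, 1245.110 and 1245.121.
4. State the denominator of the recurrence tables. The general rule in protocol Section 9.7 and SAP Section 4 points to all treated patients, but the recurrence entries do not say so.

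In the likelier case, where they can be counted, the cost is one corrected sentence, a denominator statement and one stratified line or footnote. In the other case a stated objective is narrowed. That may need another round of PRAC comments, since the SAP history table links each revision to such comments. What is given up is reliance on a crude pooled SAF-M1 recurrence figure.

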## **9.10 OTHER ASPECTS**

### **9.10.1 Data quality assurance**

Data-quality assurance measures according to BI standards have been implemented in study 1245.25 (see details in CTR [[c02695839](#), Section 9.6]) and will be implemented in studies 1245.110 and 1245.121 (see CTPs [[c03946327](#), [c09098452](#), Section 8.2]).

The collection of LLA events is detailed in [Section 9.3.2.1](#).

## **9.10.2 Study records**

Electronic CRFs via remote data capture were used for all patients in study 1245.25 [[c02695839](#), Section 9.6] and will be used in studies 1245.110 and 1245.121 [[c03946327](#), [c09098452](#), Section 8.3] according to BI standards.

### **9.10.2.1 Source documents**

Source documents have been documented in study 1245.25 [[c02695839](#), Section 9.6] and will be documented in studies 1245.110 and 1245.121 [[c03946327](#), [c09098452](#), Section 8.3.1] according to BI standards.

### **9.10.2.2 Direct access to source data and documents**

Direct access to source data and documents is described for study 1245.25 [[c02695839](#), Section 9.6] and for studies 1245.110 and 1245.121 [[c03946327](#), [c09098452](#), Section 8.3.2].

## **9.10.3 Completion of study**

The EC/competent authority in each participating EU member state has been notified about the end of the study 1245.25, and will be notified about the end of the studies or early termination of the studies 1245.110 and 1245.121.

## **10. PROTECTION OF HUMAN SUBJECTS**

Study 1245.25 was carried out in compliance with the protocol, the principles laid down in the Declaration of Helsinki, in accordance with the ICH Harmonised Tripartite Guideline for Good Clinical Practice (GCP) and in accordance with applicable regulatory requirements. Contract research organisations (CROs) involved in trial conduct could follow their own standard operating procedures (SOPs) as long as the SOP content was consistent with BI standards, GCP requirements, and requirements of local law [[c02695839](#), Section 5].

Studies 1245.110 and 1245.121 will be carried out in compliance with the protocol, the principles laid down in the Declaration of Helsinki, in accordance with the ICH Harmonised Tripartite Guideline for GCP and in accordance with applicable regulatory requirements [[c03946327](#), [c09098452](#), Section 8].

### **10.1 STUDY APPROVAL, PATIENT INFORMATION, AND INFORMED CONSENT**

Standard procedures for study approval, patient information, and informed consent have been or will be applied. See details in CTR 1245.25 [[c02695839](#), Section 5] and CTPs 1245.110 and 1245.121 [[c03946327](#), [c09098452](#), Section 8.1].

### **10.2 STATEMENT OF CONFIDENTIALITY**

Standard procedures to ensure confidentiality have been or will be applied. See details in CTR 1245.25 [[c02695839](#), Section 5.3] and CTPs 1245.110 and 1245.121 [[c03946327](#), [c09098452](#), Section 8.5].

## **11. MANAGEMENT AND REPORTING OF ADVERSE EVENTS/ADVERSE REACTIONS**

### **11.1 DEFINITIONS OF ADVERSE EVENTS**

The definitions of AEs follow ICH E6 (Good Clinical Practice) and BI standards and can be found in CTR 1245.25 [[c02695839](#), Section 9.5.3.2.1] and CTPs 1245.110 and 1245.121 [[c03946327](#), [c09098452](#), Section 5.3.7.1].

In the protocols of the ongoing studies 1245.110 and 1245.121, events leading to LLA are defined as AESIs and include any event leading to a lower-limb procedure of amputation, auto-amputation, or disarticulation. Amputation is defined as a resection of a limb through a bone. Auto-amputation is a spontaneous separation of non-viable portion of the lower limb. Disarticulation is a resection of a limb through a joint. The following procedures are not included in the definition of events leading to LLA: debridement (removal of callus or dead tissue), procedures on a stump (such as stump revision, drainage of an abscess, wound revision, etc.), and other procedures (such as nail resection or removal) without a concomitant resection of a limb (amputation or disarticulation). The definitions are consistent with the 2015 guidance from the [REDACTED] (website: [REDACTED]).

Each lower-limb amputation, disarticulation, or auto-amputation should be reported separately. The SAE report for this type of AESI is to include the date of the procedure, the level of amputation or disarticulation, the medical condition(s) leading to the procedure, and if the patient had any of the known risk factor(s) for lower-limb amputation.

In the completed study 1245.25, events related to LLA were not defined as AESIs in the protocol, but were identified via a systematic search of the study database (see [Section 9.3.2.1](#)).

### **11.2 ADVERSE EVENT AND SERIOUS ADVERSE EVENT COLLECTION AND REPORTING**

All data including (S)AEs have been (1245.25) or are collected (1245.110 and 1245.121) in the context of the 3 trials and no additional AE collection is required for this meta-analysis.

The collection and reporting of (S)AEs follow BI standards and can be found in CTR 1245.25 [[c02695839](#), Section 9.5.3.2.2] and CTPs 1245.110 and 1245.121 [[c03946327](#), [c09098452](#), Section 5.3.7.2]. All (S)AEs collected in the trials included in this meta-analysis have been reported in the CTR 1245.25 and will be reported in the CTRs for 1245.110 and 1245.121.

In studies 1245.110 and 1245.121, events leading to LLA are defined as AESIs. The collection and reporting of AESIs follow the rules for SAEs, which require expedited reporting on the BI SAE form (within 24 hours) and the collection of post-study events.

### **11.3 REPORTING TO HEALTH AUTHORITIES**

Adverse event reporting to regulatory agencies will be done by the MAH according to local and international regulatory requirements. Reporting of (S)AEs to health authorities has been

Proprietary confidential information © 2019 Boehringer Ingelheim International GmbH or one or more of its affiliated companies

(1245.25) or is carried out (1245.110 and 1245.121) in the context of the 3 trials and no additional reporting is required for this meta-analysis.

## **12. PLANS FOR DISSEMINATING AND COMMUNICATING STUDY RESULTS**

The meta-analysis report will be submitted to the EMA in line with the agreed milestone.

## **ANNEX 1. LIST OF STAND-ALONE DOCUMENTS**

Number	Document Reference Number	Date	Title
1	c16853237-05	10 Apr 2019	1245.171: A Meta-Analysis of Amputation Risk in empagliflozin studies (1245.25, 1245.110, 1245.121). Statistical Analysis Plan for trial 1245.171
2	c03946327-03	19 Jul 2018	A phase III randomised, double-blind trial to evaluate efficacy and safety of once daily empagliflozin 10 mg compared to placebo, in patients with chronic Heart Failure with preserved Ejection Fraction (HFpEF). EMPEROR-Preserved, CTP 1245.110
3	c09098452-03	18 Jul 2018	A phase III randomised, double-blind trial to evaluate efficacy and safety of once daily empagliflozin 10 mg compared to placebo, in patients with chronic Heart Failure with reduced Ejection Fraction (HFrEF). EMPEROR-Reduced, CTP 1245.121
4	c02695839-01	12 Oct 2015	A Phase III, multicentre, international, randomised, parallel group, double blind cardiovascular safety study of BI 10773 (10 mg and 25 mg administered orally once daily) compared to usual care in type 2 diabetes mellitus patients with increased cardiovascular risk. CTR 1245.25.
